7.6.5.2 Time to Clinical Improvement

Clinical progression will be assessed using the WHO Ordinal Scale ([Table 2](#)). Baseline is defined as last non-missing assessment prior to the first dose of study drug. Frequency counts and percentages will be presented by visit for WHO Ordinal Scale.

Table 2 Who Ordinal Scale

Patient State	Descriptor	Score
Uninfected	Uninfected; no viral RNA detected	0
Ambulatory mild disease	Asymptomatic; viral RNA detected	1
	Symptomatic; independent	2
	Symptomatic; assistance needed	3
Hospitalized: moderate disease	Hospitalized; no oxygen therapy*	4
	Hospitalized; oxygen by mask or nasal prongs	5
Hospitalized: severe disease	Hospitalized; oxygen by NIV or high flow	6
	Intubation and mechanical ventilation, $pO_2/FiO_2 \geq 150$ or $SpO_2/FiO_2 \geq 200$	7
	Mechanical ventilation $pO_2/FiO_2 < 150$ ($SpO_2/FiO_2 < 200$) or vasopressors	8
	Mechanical ventilation $pO_2/FiO_2 < 150$ and vasopressors, dialysis, or ECMO	9
Dead	Dead	10

Clinical improvement is defined as at least 1-point decrease from baseline in WHO Ordinal Scale. Time to clinical improvement will be analyzed in the subset of ITT subjects with baseline WHO Ordinal Scale of 2 or 3. The time to clinical improvement is defined as the time (in days) from Day 1 to the first date of clinical improvement. Subjects didn't achieve clinical improvement will be censored at the date of last assessment of WHO Ordinal Scale. The median (95% CI) time to clinical improvement will be presented by treatment groups using the Kaplan-Meier method.

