3 INTRODUCTION

3.1 Coronavirus-19 (COVID-19)

Beginning in December 2019, Chinese scientists isolated a novel coronavirus, severe acute respiratory syndrome coronavirus 2 (SARS-CoV-2) from patients with virus-infected pneumonia which was later designated as coronavirus disease 2019 (COVID-19) by the World Health Organisation (WHO) (Zhou et al., 2020 [2]; Phelan et al., 2020 [3]).

Approximately 14% of those affected with this virus will develop severe disease requiring hospitalization and oxygen support; 5% will require admission to the intensive care unit (Handel et al., 2020 [4]). Severe cases may be complicated by acute respiratory disease syndrome (ARDS), sepsis and septic shock, and multi-organ failure, including acute kidney injury and cardiac injury. Risk factors for death include older age and co-morbid disease such as hypertension and diabetes (Zhou, et al., 2020 [2]). This means that most patients will be treated as out-patients. Reducing viral load in this environment is critically important for both the subjects themselves by preventing worsening of symptoms and possibly avoiding hospitalization, but also to reduce the transmission of the disease to others in the patients' households and their communities.

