7.6.4 Secondary Clinical Analysis

7.6.4.1 Hospital Admission

Subjects requiring hospital admission as an inpatient for >24 hours will be analyzed in the ITT population. Number and proportion of subjects requiring hospital admission along with 95% exact binomial CI (Clopper-Pearson) will be presented for each treatment group. Two-sided 95% CI will also be presented for the difference in percent of subjects requiring hospital admission between treatment groups with an approximate normal distribution. The Fisher's exact test will be used to compare the proportion of subjects requiring hospital admission. The two-sided p-value for the Fisher's exact test will be presented.

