7.6.5 Exploratory Clinical Analysis

7.6.5.1 Time to Resolution of Symptoms

Symptom assessment will use a checklist provided to the subject with symptoms such as sore throat, cough, gastrointestinal symptoms (vomiting, diarrhea), anosmia, dysgeusia, other (specify), etc. Symptoms start date, end date (or ongoing), severity "None", "Mild", "Moderate", or "Severe" and symptoms status "Resolved", "Ongoing", or "Returned to Baseline" will be collected.

Resolution of symptoms is defined as new COVID-19 symptoms are completely resolved (i.e. status of "Resolved") and pre-existing non-COVID-19 symptoms return to baseline (i.e. status of "Returned to Baseline") reported on the eCRF of "COVID-19 Symptom Assessment". The time to resolution of symptoms is defined as the time (in days) from Day 1 to the first date where symptoms have been resolved. Subjects didn't achieve resolution of symptoms will be censored at the date of last assessment of symptoms. The median (95% CI) time to resolution of symptoms will be presented by treatment groups using the Kaplan-Meier method for the ITT population.

Statistical Analysis Plan

Sponsor Name: Clear Creek Bio, Inc.
Sponsor Protocol ID: CCB-CRISIS-02

Covance Study ID: 000000207395

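### Time to clinical improvement and time to symptom resolution censor subjects who die at their last assessment, so Kaplan-Meier treats them as still able to improve

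*SAP*

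**What the plan says.** SAP 7.6.5.2 sets the event: "Clinical improvement is defined as at least 1-point decrease from baseline in WHO Ordinal Scale". The analysis set is the ITT subjects with a baseline score of 2 or 3. Those who do not reach the event "will be censored at the date of last assessment of WHO Ordinal Scale". The planned summary is this: "The median (95% CI) time to clinical improvement will be presented by treatment groups using the Kaplan-Meier method". No between-group test is stated. The same section also plans a by-visit table of the scale, on which score 10 is death: "Frequency counts and percentages will be presented by visit for WHO Ordinal Scale".

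SAP 7.6.5.1 follows the same pattern: "Subjects didn't achieve resolution of symptoms will be censored at the date of last assessment of symptoms". The summary is again a Kaplan-Meier median with its interval, in ITT.

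Three other places bear on the point. SAP 6.2 rules out imputing missing efficacy data outside the statistical models, so nothing supplies a score after death. SAP 7.6.4.2 analyses all-cause mortality separately in ITT, with exact intervals and Fisher's exact test. Protocol v5.0, Section 9.7, keeps scheduled evaluations going after study drug is stopped unless consent is withdrawn.

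**The concern.** Kaplan-Meier is valid for a time-to-improvement curve when a censored subject has the same future chance of improving as the subjects still at risk at that time. Someone who withdraws consent on Day 10 may meet that condition. Someone who dies on Day 10 cannot. Under the rule as written both are handled identically: each leaves the risk set at the last assessment, and the later improvement rate among survivors is in effect credited to them.

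The resulting curve describes a world in which nobody dies. That is not what a reader takes from a median time to improvement in an ITT subset. The error favours whichever arm has more deaths, which is the wrong direction for a measure of benefit. The same reasoning applies to symptom resolution.

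**Working it through.** The plan contains no figure to reproduce: SAP 2.3 says no formal sample size calculation was made, and no improvement or death rate is given. The check is therefore an illustration under stated assumptions.

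**Inputs from the documents.** About 50 subjects per arm (Protocol synopsis). Post-baseline WHO assessments on Days 8, 15, 22 and 29 (Schedule of Events). Censoring rule from SAP 7.6.5.2. For simplicity all 50 are taken to be in the baseline 2-or-3 subset.

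**Assumed inputs.** Cumulative improvement F among subjects who do not die, on Days 8, 15, 22 and 29:

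- fast: 40%, 65%, 80%, 90%
- middle: 25%, 51%, 70%, 82%
- slow: 15%, 35%, 51%, 65%

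k subjects of n = 50 die without having improved. Expected (fractional) counts are used.

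**Formulas.**

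- Deaths kept at risk to Day 29: improved by day t = F(t) × (n − k)/n. With no other loss, this equals the cumulative incidence with death as a competing event.
- SAP rule, last assessment on Day 1: improved by day t = F(t), because those who die drop out before any event. The excess is F(t) × k/n.
- SAP rule, last assessment on Day 8: improved by day t = 1 − [1 − F(8) × (n − k)/n] × [1 − F(t)]/[1 − F(8)]. If the last assessment was Day 15, put 15 in place of 8.

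**One case in full: middle rates, k = 2, last assessment on Day 8.** Day 8: 12 of 50 improve, leaving 0.76 not improved. The two who die are then censored. Day 15: 36 at risk, 12.48 improve, 0.76 × (1 − 12.48/36) = 0.497. Day 29 by the formula: 1 − 0.76 × 0.18/0.75 = 0.818. Kept at risk: 0.82 × 48/50 = 0.787. Excess: 3.0 points.

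**Two deaths, last assessment on Day 8:**

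| Rates | Day 29, SAP rule | Day 29, kept at risk | Excess (points) | Median, SAP rule | Median, kept at risk |
|---|---|---|---|---|---|
| Fast | 89.7% | 86.4% | 3.3 | Day 15 | Day 15 |
| Middle | 81.8% | 78.7% | 3.0 | Day 15 | Day 22 |
| Slow | 64.8% | 62.4% | 2.4 | Day 22 | Day 29 |

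**Range for one death.** Largest: fast rates, last assessment on Day 1, 0.90/50 = 1.8 points. Smallest: slow rates, last assessment on Day 15, 1 − (1 − 0.35 × 0.98) × 0.35/0.65 = 0.646 against 0.65 × 0.98 = 0.637, or 0.9 points. Hence about 1 to 2 points per death.

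**Why the median moves in two rows.** In the middle case the Day 15 estimate is 50.3% under the SAP rule and 49.0% kept at risk. In the slow case the Day 22 figures are 50.7% and 49.0%. The curve straddles 50% only because the assumed rates put it there. In the fast case it is well above 50% at Day 15 either way, and the median does not move.

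**Between arms.** Middle rates, two deaths in one arm (last assessment on Day 8) and none in the other. The SAP rule gives 81.8% against 82.0%, which look alike. Kept at risk, it is 78.7% against 82.0%, a gap of 3.3 points. With equal deaths and equal rates the two arms shift together and the difference is unaffected.

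**How likely any death is.** For assumed death rates of 0.2% to 5%, 0.2 to 5 deaths are expected in 100 subjects. The chance of at least one is 1 − 0.998^100 = 18% to 1 − 0.95^100 = 99%.

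**The case against.** The strongest reply is that the plan does not hide deaths. Mortality is a secondary ITT endpoint with its own test, and score 10 appears in the by-visit WHO table. The two affected endpoints are exploratory, and Protocol Section 11 makes all testing exploratory. Only medians are planned, so the Day 29 percentages above measure the bias and are not outputs the SAP commits to. All of this stands, and it limits the importance of the point. It does not make the improvement and resolution curves correct.

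A second reply is that a score of 10 might be entered at every visit after death, so that the last assessment would be Day 29. The SAP does not say so and bars imputation. The symptom checklist described in 7.6.5.1 has no category for death at all.

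A reader might infer more than the documents support:

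- **That subjects who worsen are lost in the same way.** No section says assessments stop on admission. Protocol 9.7 and SAP 6.2 require them to continue, and WHO scores 4 to 9 exist to score inpatients. A hospitalised subject who is still assessed stays at risk, as intended.
- **That loss could reach 14%.** The Protocol's statement, "Approximately 14% of those affected with this virus will develop severe disease requiring hospitalization and oxygen support; 5% will require admission to the intensive care", is background on everyone infected. It is neither a loss rate nor a planning assumption.
- **That the admission endpoint is wrong because a death without a stay over 24 hours counts as not admitted.** SAP 7.6.4.1 analyses admission as the Protocol defines it: "Subjects requiring hospital admission as an inpatient for >24 hours will be analyzed in the ITT population". Mortality is reported beside it in the same population. A combined summary would be useful, but its absence is not an error.
- **That clinical outcomes in general look better than they are.** Mortality is unaffected, and so is the by-visit table.

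**Conclusion.** The point holds for SAP 7.6.5.1 and 7.6.5.2. The rule as written covers every subject without the event, makes no exception for death, and so can overstate improvement and resolution. This is a wrong stated rule, not merely a missing detail.

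Its size is modest. It depends on assumed improvement rates and on a number of deaths that the documents do not predict. The arithmetic was done on the WHO visit days. The direction is the same for symptom resolution, but its size there was not calculated separately. The weight is that of a cheap correction to two exploratory analyses. The primary viral load analysis is untouched.

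**What to change.** **Required.** In both sections, state that a subject who dies without the event remains in the risk set as not improved or not resolved and is censored at Day 29. Equivalently, report cumulative incidence with death as a competing event. SAP 7.1 bases times on actual dates and the final visit has a window of ±2 days. The censoring day for deaths should therefore be no earlier than the end of that window, so that events at late final visits are still counted against them.

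**Sensitivity analysis.** Treat subjects who are hospitalised and have no later assessment in the same way. This should not be the main rule: it is a worst-case assumption, and some of those subjects will have recovered.

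**Optional.** In 7.6.4.1, show admission over 24 hours or death by Day 29 beside the admission rate.

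**Cost.** A sentence in each section, a derivation rule and one additional run. No new data are needed. SAP Section 8 already foresees a further approved version that could carry the change.

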4.3 EXPLORATORY OBJECTIVES

Through Day 29:

- To determine time to viral clearance (two consecutive negative tests);
- To determine time to resolution of new onset COVID-19-related clinical symptoms and pre-existing non-COVID-19 symptoms returned to baseline;
- To determine time to clinical improvement as measured by a favorable shift in the WHO Ordinal Scale score for the subset of subjects with baseline WHO Ordinal Scale of 2 or 3 for brequinar subjects compared to subjects who received placebo.

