5 TRIAL DESIGN

This will be a phase II randomized, placebo-controlled, double blind, multi-center study with approximately 100 subjects. All subjects will receive standard of care per (SOC) institutional guidelines for treatment of patients with COVID-19 infection. In addition to SOC, the subjects will self-administer one capsule once daily for 5 days.

Subjects must have at least one symptom consistent with SARS-CoV-2 infection according to the investigator and first symptom onset must be \leq 7 days prior to first dose. Subjects will have a Screening Visit followed as soon as possible with Study Day 1. Study procedures are presented in detail in [the Schedule of Events \(Appendix 15.1\)](#). Study visits (virtual or in person) will take place at Screening and on Study Days 1 - 8, 12, 15, 22, and 29. The visits that include bloodwork must be conducted at the study site or arrangements made for sample collection at the subject's home or other appropriate location. Other visits/visit activities for that visit may be conducted remotely using telephone, telemedicine or other remote technique. Subjects are to self-collect a viral load sample. Subjects will obtain their own respiratory rate, heart rate, body temperature and SpO2 during telemedicine visits or study staff will collect these parameters during an in-person visit at the clinic or subject's home. The symptom assessment can be conducted with the study staff via telemedicine or in the clinic on Days 1, 4, 8, 12, 15, 22, and 29. The site will also have a telephone call with the subject on Study Days 2, 3, 5, 6, and 7 for changes in concomitant medications and assessment of adverse events, especially those that may indicate thrombocytopenia (see Section 10.8) and mucositis. An in-person visit will be conducted (at the clinic or home visit) at Screening and on study Days 1, 8, 15, and 29; in-person visits may be combined with telemedicine or telephone visits if all required study visit activities cannot be completed by the in-person personnel. Telemedicine only visits will be conducted by site staff on study Days 4, 12, and 22.

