15 APPENDICES

15.1 Appendix A: CCB-CRISIS-02 Schedule of Events

CCB-CRISIS-02 Schedule of Events Windows are relative to first dose time Procedures	Screen (D -7 to -1) IPV ^f	D1 IPV	D2, 3 (± 8 hrs) TC ^f	D4 (± 8 hrs) TM	D5,6,7 (± 8 hrs) TC	D8 (± 8 hrs) IPV+TM	D12 (± 1 day) TM	D15 (± 1 day) IPV+TM	D22 (±1 day) TM	Final Visit D29 (± 2 days) IPV+TM
Informed Consent (note Date and Time)	X									
AE/Concomitant Medications (dose, route, duration or ongoing)	X	X	X	X	X	X	X	X	X	X
Medical history (relevant within one year or ongoing)/ History of current illness (date of symptom onset or change in baseline co-morbidity thought to be due to COVID-19 infection)	X									
Demographics (subject reported height and weight, date of birth, gender, race, ethnicity)	X									
Check for Physical Exam abnormalities (subject self-reported)	X									
Pregnancy Test (WOCBP)	X (serum)									X (urine)
Hematology/Chemistry ^a	X	X				X		X		
Vital Signs ^b	X	X		X		X	X	X	X	X
Symptom Assessment ^c	X	X		X		X	X	X	X	X
SARS-CoV-2 RT-PCR ^d	X									
Viral load sample (pre-dose Day 1) ^e		X		X		X	X	X	X	X
Hospital Status						X		X	X	X
WHO Ordinal Scale Assessment		X				X		X	X	X
Confirm Eligibility		X								
Randomize subject and dispense Study Medication		X								
Study drug administration ^f		X	X	X	X D5 Only					
Drug Accountability						X				

^aDo not repeat if within 48h of Day 1 visit. Send to Covance Central Laboratory Services (CCLS) for analysis.

^bVital signs include heart rate, respiratory rate, body temperature, and SpO2. Subject will be provided with a thermometer and pulse oximeter with heart rate monitoring capability. Training will be provided during the first visit. Vital signs parameters will be observed and recorded by study staff via telemedicine or in person (IPV) (at the study site or home visit).

^cSymptom Assessment will capture symptoms such as sore throat, cough, GI symptoms (vomiting, diarrhea), anosmia, dysgeusia, other (specify), etc. Severity None, Mild, Moderate, or Severe will be collected. Symptom(s) onset date must be within 7 days of first dose.

^dDocumentation of a positive SARS-CoV-2 result from RT-PCR or other FDA-approved test is required to qualify for Screening.

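### WHO scoring only on Days 8, 15, 22 and 29 makes the median times to clinical improvement about 2 to 5 days late and distorts the gap between arms in either direction, and no between-arm comparison is planned

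*SAP*

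**What the plan says.** Protocol 4.3 sets the objective: "To determine time to clinical improvement as measured by a favorable shift in the WHO Ordinal Scale score", in subjects with a baseline score of 2 or 3, for brequinar compared with placebo.

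SAP 7.6.5.2 defines the event: "Clinical improvement is defined as at least 1-point decrease from baseline in WHO Ordinal Scale". The event is dated at the first assessment that shows the fall, counted from Day 1, and a subject who never improves is censored when last scored. The planned summary is: "The median (95% CI) time to clinical improvement will be presented by treatment groups using the Kaplan-Meier method". The same section also plans by-visit counts and percentages of the scale. It plans no test, no hazard ratio and no method for interval-censored times.

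In Protocol v5.0 Appendix 15.1 the row "WHO Ordinal Scale Assessment" is marked on Days 1, 8, 15, 22 and 29. SAP Table 1 also has no entry on Day 4 or Day 12. Contacts on those days already exist. Protocol section 5 says: "Telemedicine only visits will be conducted by site staff on study Days 4, 12, and 22". It schedules the symptom assessment on Days 4 and 12 too. Day 22 is therefore a remote visit at which the scale is scored.

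**The concern.** Dosing ends on Day 5 and the first post-baseline score comes on Day 8, so no improvement can be dated during treatment or in the days just after it. From then on, a subject who improves between visits waits up to a week to be counted. The Kaplan-Meier method treats the detection date as the event date. Both medians are therefore shifted late, by amounts that depend on where each falls in the grid, and their difference need not resemble the true one.

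The steps that matter here can be judged on a call. From a score of 2, improvement is loss of symptoms; from 3, it is no longer needing assistance. The scale is already scored remotely on Day 22, and the documents give no reason for leaving out Days 4 and 12.

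The trial's stated purpose is to inform the design of later studies. A timing estimate that is off by days, or an arm gap created or erased by the visit grid, is a poor input for that.

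**Working it through.** **Inputs from the documents.** About 50 per arm (Protocol 7.1). Event, dating and censoring from SAP 7.6.5.2. Actual dates rather than visit days for time-to-event endpoints (SAP 7.1). Windows in Protocol v5.0 Appendix 15.1: 8 hours either side at Days 4 and 8 (treated here as the same calendar day), 1 day at Days 12, 15 and 22, and 2 days at Day 29.

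**Assumptions.** The documents give no expected time to improvement and no effect size, so there is no planned figure to reproduce. True times were taken as exponential, with a Weibull (shape 1.3) check and a hazard ratio of 1.5. Improvement persists and there is no dropout.

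**Detection delay by arithmetic.** If improvement is equally likely at any time, the mean delay is Σg² / (2Σg), where g are the gaps between scores.
- Planned gaps 7, 7, 7, 7. Through Day 15: (49 + 49) / 28 = 3.5 days.
- With Days 4 and 12 the gaps are 3, 4, 4, 3, 7, 7. Through Day 15: (9 + 16 + 16 + 9) / 28 = 1.8 days.
- Through Day 29: 196 / 56 = 3.5 days against 148 / 56 = 2.6 days.

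**Simulation** (20,000 trials, exponential times, v5.0 windows). Medians are study days, placebo/brequinar. The last three columns add Days 4 and 12.

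| True medians | Reported | Late by | Identical | 5+ days apart | Reported | Identical | 5+ days apart |
|---|---|---|---|---|---|---|---|
| 4.0/3.0 | 8.0/8.0 | 4.0/5.0 | 100% | 0% | 5.8/4.0 | 55% | 0% |
| 6.0/4.3 | 8.2/8.0 | 2.2/3.7 | 97% | 3% | 8.0/6.6 | 62% | 1% |
| 8.0/5.7 | 10.8/8.1 | 2.8/2.4 | 56% | 44% | 9.6/7.9 | 54% | 7% |
| 10.0/7.0 | 13.8/9.1 | 3.8/2.1 | 18% | 73% | 11.9/8.6 | 15% | 34% |
| 12.0/8.3 | 15.5/11.4 | 3.5/3.1 | 13% | 51% | 14.0/10.0 | 9% | 42% |
| 15.0/10.3 | 18.4/14.1 | 3.4/3.8 | 13% | 51% | 17.8/12.2 | 7% | 53% |

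**Lateness.** The range is 2.1 to 5.0 days now. With Days 4 and 12 it is 1.0 days (4.0 − 3.0) to 2.8 days (17.8 − 15.0).

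**Difference between arms.** At 8.0/5.7 the true gap is 2.3 days. The reported gap is within 1 day in 56% of trials and 5 or more days in 44%, with nothing between. With times observed exactly, the medians would be within 1 day in 20%. At 10.0/7.0 the true gap is 3.0 days and the mean reported gap is 13.8 − 9.1 = 4.7 days. With no treatment effect and both true medians at Day 10, the reported medians are 5 or more days apart in 26% of trials, falling to 14% with the added scores.

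**Check with Weibull times.** Placebo medians are 1.8 to 3.8 days late now and 1.4 to 2.8 days late with the added scores. For true Day 9 against 6.9, a gap of 2.1 days, the reported gap is 5 or more days in 71% of trials now and 13% after. Log-rank power, using nominal visit days, is 0.46–0.49 now and 0.47–0.50 after.

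**The case against.** A reader might infer that the median can take only four values and will often be the same in both arms, so that real differences are hidden. The documents do not support that. SAP 7.1 uses actual dates, and the windows spread the events around each visit. In the Weibull check, counting nominal days gives exact ties in 78% of trials (true Day 13 against 9.8) and 55% (Day 11 against 8.3); with actual dates both fall to about 17–18%. Ties are near-certain (94–100%) only with both true medians at about Day 6 or earlier and the v5.0 Day 8 window. With no expected times in the documents, nobody can say how often that would happen. The distortion also runs the other way when the medians straddle a visit.

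Nor does the SAP report bare medians alone. It plans confidence intervals and the by-visit distribution of the scale, which does not depend on dating the event. SAP 7.6.5.1 also plans time to symptom resolution from recorded symptom dates. That largely covers the step out of score 2, though not the step from 3 to 2.

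The endpoint is exploratory and the Protocol treats all analyses as descriptive, so no decision rests on these medians. That limits the weight of the point but does not explain the missing comparison: time to viral clearance is also exploratory and receives a log-rank test (SAP 7.6.3.1, by reference to 7.6.2).

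Finally, adding scores is not a full cure. It changes little when the true median lies in Days 4 to 8 or after Day 15. Because a single 1-point fall counts without confirmation, two more looks slightly raise the chance of counting a transient dip.

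**Conclusion.** The concern holds in a limited form. The schedule interval-censors improvement on a roughly 7-day grid. Reported medians run about 2 to 5 days late, and their difference tends towards about zero or about a week depending on where the true medians fall. Separately, a comparative objective has no between-arm comparison in the SAP. The lateness follows from the schedule and appears in every scenario run. Its size, and the direction of distortion between arms, rest on assumed medians, hazard ratio and distribution, and on improvement persisting without dropout. This is an inexpensive improvement to an exploratory endpoint and does not threaten the primary analysis.

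**What to change.** - In Protocol Appendix 15.1, the matching synopsis schedule and SAP Table 1, mark the WHO Ordinal Scale on Days 4 and 12, scored by site staff on the calls already scheduled. Collect the score itself: the symptom checklist as described does not record need for assistance, so it cannot separate 2 from 3.
- In SAP 7.6.5.2, use all six post-baseline scores (Days 4, 8, 12, 15, 22, 29). Keep the medians and by-visit frequencies, and add an unstratified log-rank test and a hazard ratio with 95% CI, labelled exploratory.
- Optionally add an interval-censored (Turnbull) estimate. It addresses the dating problem directly and needs no new data.
- Add a sensitivity analysis on the four original visits, since subjects already past Day 4 or Day 12 will lack those scores.

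The cost is a protocol amendment across about 15 sites (with IRB approval if judged substantial), an eCRF field, two one-item scores per subject and a SAP edit. No visit is added. The SAP (4 November 2020) predates Protocol v5.0 (19 November 2020) and needs revising anyway: its Day 8 window is 1 day either side against 8 hours in v5.0. In the same revision, reconcile the subset for this endpoint, which is baseline score 2 in Protocol 6.3 but 2 or 3 in Protocol 4.3 and the SAP.
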